STATISTICS Primary Analysis Plan	Patient baseline characteristics will be analyzed with descriptive statistics (ie. mean age, % male, mean pectus severity index, etc.). Our primary outcome will be post-operative length of stay, which will be analyzed using a two-tailed unpaired t test, with results considered statistically significant for $p < 0.05$ . Secondary outcomes include post-operative pain scores, pain medication usage, and side effects. Pain scores will be analyzed with Mann-Whitney rank sum tests (to compare between groups at each time point) and Wilcoxon signed-rank test (to compare scores within groups over time), with results considered statistically significant for $p < 0.05$ . Pain medication usage between the two groups will be analyzed with two-tailed unpaired t test, again with results considered statistically significant for $p < 0.05$ . Given our small sample size and the low rate of complications with both analgesic methods, we expect very limited side effect data. A descriptive overall side effect rate will be calculated for each arm of the study, and the individual side effects will be listed in a table. A cost analysis will be performed, comparing the total cost of hospitalization between the cryoanalgesia and epidural groups. Difference in total cost will be assessed with two-tailed unpaired t test.

Rationale for Number of Subjects	
We used the UCSF Clinical & Translational Science Institute web-based sample size calculator (http://www.sample-size.net/sample-size-means/) to determine study size. Based on previous Nuss procedures over the past 2 years at our institution, we determined the mean length of hospitalization was 7 days, with a standard deviation of 1.3 days. From anecdotal data from our prior experience, as well as from speaking with other surgeons utilizing cryoablation, we expect patients in the cryoanalgesia group to have approximately 2 days shorter hospital stay. With type I error rate of 0.05 and type II error rate of 0.1 (yielding 90% power), our study would need 18 patients total. Allowing for some dropout, we will plan to enroll 20 patients to the study.

---	---

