### 8.3 Test and Control Products

#### 8.3.1 Test Product

AtriCure cryosurgical system (AtriCure, Inc., West Chester, Ohio)

The cryoprobe will be applied to the intercostal nerve under thoracoscopic visualization at the level of the incision and 2 interspaces above and below, bilaterally. The temperature and duration of cryoablation therapy is pre-set by the probe and cryosurgical system at 2 minutes to -60°C. Each nerve will receive one cycle of cryoablation.

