#### 8.3.2 Control Product

Thoracic epidural catheter will be placed by the pediatric anesthesia team prior to Nuss procedure. Catheters will be placed using sterile technique at approximately T5-6 or T6-7 interspaces; procedure specifics are dependent on the attending anesthesiologist's patient-dependent preference. Whether the patient will be awake or asleep for epidural placement will be at the discretion of the attending anesthesiologist. After placement, epidural infusion will begin with 0.1% ropivacaine and 2mcg/cc fentanyl. No bolus doses will be used.

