## 13 PROTOCOL VIOLATIONS

A protocol violation occurs when the subject or investigator fails to adhere to significant protocol requirements affecting the inclusion, exclusion, subject safety and primary endpoint criteria. Protocol violations for this study include, but are not limited to, the following:

- Failure to meet inclusion/exclusion criteria
- Interference with randomization
- Non-compliance with study drug regimen

Failure to comply with Good Clinical Practice (GCP) guidelines will also result in a protocol violation. The investigator will determine if a protocol violation will result in withdrawal of a subject.

When a protocol violation occurs, it will be discussed with the investigator and a Protocol Violation Form detailing the violation will be generated. This form will be signed by a Sponsor representative and the Investigator. A copy of the form will be filed in the site's regulatory binder and in the Sponsor's files.

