### 14.1 Data Sets Analyzed

All eligible patients who are randomized into the study and receive at least the initial analgesic application (cryoanalgesia or epidural catheter placement) and undergo Nuss procedure will be included in the analysis.

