### 14.4 Analysis of Secondary Endpoints

Secondary outcomes include post-operative pain scores, pain medication usage, and side effects. Pain scores will be analyzed with Mann-Whitney rank sum tests (to compare between groups at each time point) and Wilcoxon signed-rank test (to compare scores within groups over time), with results considered statistically significant for  $p < 0.05$ . Pain medication usage between the two groups will be analyzed with two-tailed unpaired t test, again with results considered statistically significant for  $p < 0.05$ .

Adverse events will be tabulated by treatment group and will include the number of patients for whom the event occurred, the rate of occurrence, and the severity and relationship to study drug.

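### Read as written, the plan's only analysis set would leave a patient harmed by epidural placement, whose operation is then cancelled for good, out of the adverse-event rates

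*Combined protocol and SAP*

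**What the plan says.** Section 14.1, the only place where an analysis population is defined, opens with "All eligible patients who are randomized into the study and receive at least the initial analgesic application (cryoanalgesia or epidural catheter placement") and ends with "and undergo Nuss procedure will be included in the analysis". That makes four conditions: eligible, randomized, given the initial analgesic, and operated on. The section does not confine them to efficacy, and no safety or as-treated set appears elsewhere.

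Section 14.4 covers harms: "Adverse events will be tabulated by treatment group and will include the number of patients for whom the event occurred, the rate of occurrence", followed by severity and relationship to treatment. The synopsis adds: "A descriptive overall side effect rate will be calculated for each arm of the study". Neither gives a denominator.

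The two methods are delivered at different times. Section 8.3.2: "Thoracic epidural catheter will be placed by the pediatric anesthesia team prior to Nuss procedure". Section 8.3.1: "The cryoprobe will be applied to the intercostal nerve under thoracoscopic visualization", which places it within the operation.

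Collection is broader than the analysis set. Section 9.1.6 captures AEs for the whole study, and Section 11.2.1 collects serious adverse events (SAEs) from consent to the last visit and has them reported to the IRB. Section 13 lists "Failure to meet inclusion/exclusion criteria" among protocol violations and leaves withdrawal to the investigator.

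**The concern.** A safety table normally counts everyone exposed to the intervention. Here the only stated rule also requires something that happens after exposure, namely that the operation takes place. A serious complication of epidural placement could itself be the reason for cancelling the operation, so the harm could remove the patient from the table meant to report it.

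The eligibility condition raises a similar but weaker worry. The exclusions in Section 6.3 include bleeding dyscrasias and major anesthetic risk factors. A patient treated before such a condition was recognised may be at higher risk of harm, and could be left out for that reason.

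Side effects are a stated secondary endpoint (Section 5.2) and AE incidence is the safety evaluation (Section 5.3). The synopsis expects few side effects in a trial this small, so a single case could be most of the safety evidence in one arm.

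**Working it through.** **The plan's own figure.** The point is about wording, and no stated figure depends on it. For completeness, the sample size in Section 14.5 reproduces. With a difference of 2 days, SD 1.3, two-sided alpha 0.05 and 90% power, n per arm = 2 × (1.960 + 1.282)² × 1.3² / 2² = 2 × 10.51 × 1.69 / 4 = 8.88. This rounds up to 9 per arm, or 18 in total. Enrolment is 20 at 1:1, hence 10 per arm (Sections 4.1 and 8.1), and withdrawals are not replaced (Section 12.4).

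**Applying the rule in 14.1 to patients exposed to a study method:**

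| Situation | Exposed? | In the 14.1 set, as written? |
|---|---|---|
| Epidural placed, operation performed | Yes | Yes |
| Epidural placed, operation postponed but later performed | Yes | Probably; 14.1 sets no time limit |
| Epidural placed, operation cancelled and never performed | Yes | No |
| Cryoprobe applied, operation completed | Yes | Yes |
| Cryoprobe applied, operation stopped before the repair is complete | Yes | Unclear; the text does not say whether this counts as undergoing the procedure |
| Either method given, criterion later found to be breached | Yes | Depends on whether eligibility is judged at entry or afterwards |

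The third row is the clear loss, and it belongs to the epidural arm. The fifth is the possible counterpart in the cryoanalgesia arm. It needs an operation already under way to be abandoned.

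**Size, as an illustration.** The documents give no probability for these events, so the number of cases is an assumption. Exact (Clopper-Pearson) 95% intervals are used. For 0 events in n, the upper limit is 1 − 0.025^(1/n).

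- One of 10 epidural patients harmed and excluded: the table shows 0/9 = 0%, upper limit 1 − 0.025^(1/9) = 33.6%. Counting all exposed gives 1/10 = 10% (0.3% to 44.5%).
- Two of 10 harmed and excluded: 0/8 = 0%, upper limit 1 − 0.025^(1/8) = 36.9%. Counting all exposed gives 2/10 = 20% (2.5% to 55.6%).

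In both scenarios each omitted case moves the reported rate by 10 percentage points. The intervals overlap heavily, so what changes is the reported count and point estimate, not a formal inference.

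**The case against.** The strongest reply is that Section 14.1 never mentions AEs. It could be meant as the efficacy set, with harms tabulated as collected; Section 14.4 does not itself restrict the AE table to the 14.1 patients. This stands in part: the link is an inference from 14.1 being the only set and being worded without limit. But on the reply's reading the AE rates have no stated denominator, and the same sentence would still be needed.

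Four further limits stand:

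- **Arm and direction.** A reader might infer that the loss can occur only in the epidural arm and that the comparison is therefore biased in its favour. The documents do not support this. Section 8.3.1 does not say at what stage of the operation the cryoprobe is used, and Section 10.2 lists the initial analgesic and the procedure together for both arms. An operation abandoned after freezing is conceivable. The supportable wording is that the loss falls mainly on the epidural arm and could favour it.
- **Postponement.** Only a cancelled operation that is never performed clearly excludes the patient.
- **Eligibility.** Section 4.1 applies the criteria at entry, and Section 13 leaves withdrawal for a breach to case-by-case judgement. Automatic removal of a patient later found ineligible is one reading, not a stated rule.
- **Visibility.** A denominator of 9 in an arm of 10 tells a careful reader that someone is missing. The synopsis also plans a listing of individual side effects and ongoing committee review of SAEs. It would be wrong to infer that the event vanishes from the trial's records.

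Finally, Section 14 promises a detailed SAP before final analysis, which could add a safety set. That limits the problem without resolving it, since the present text contains none. In an open-label trial, a population fixed now is more credible than one chosen once the events are known.

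**Conclusion.** The point holds as a defect of modest size. The one stated rule, followed literally, makes the AE and side-effect rates conditional on an event after exposure. It would omit an epidural patient whose operation is permanently cancelled after a placement harm. The eligibility limb is less certain and secondary.

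This rests on two assumptions: that the 14.1 set is the one used for the harm tables, and that such a case occurs. The second is probably uncommon, as the synopsis expects few complications with either method. If one does occur, the reported epidural rate would be 0/9 rather than 1/10. The planned harm summaries are descriptive, and the primary comparison of length of stay is not affected by this point.

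**What to change.** Add to Sections 14.1 and 14.4, and carry into the SAP, that side effects, AEs and SAEs are tabulated in a safety set. This set contains every patient in whom epidural placement was attempted or the cryoprobe was applied, regardless of eligibility and of whether the Nuss procedure followed, grouped by method received. Leave the efficacy set to its own rule.

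Attempted placement is named because 14.1 counts catheter placement, so a patient harmed by a failed attempt might otherwise not qualify. Grouping by method received matters only if someone receives a method other than the one assigned; the documents do not suggest that this is expected.

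The cost is about two sentences. No new data are needed, because Sections 9.1.6 and 11.2.1 already collect the events. The small downside is that the safety and efficacy denominators may differ by a patient, which a footnote can explain.

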### 14.2 Demographic and Baseline Characteristics

The following demographic variables at screening will be recorded: gender, age, race, height and weight, medical comorbidities, severity of pectus excavatum deformity.

### 14.3 Analysis of Primary Endpoint

Our primary outcome will be post-operative hospital length of stay, which will be analyzed using a two-tailed unpaired t test, with results considered statistically significant for  $p < 0.05$ .

### 14.4 Analysis of Secondary Endpoints

Secondary outcomes include post-operative pain scores, pain medication usage, and side effects. Pain scores will be analyzed with Mann-Whitney rank sum tests (to compare between groups at each time point) and Wilcoxon signed-rank test (to compare scores within groups over time), with results considered statistically significant for  $p < 0.05$ . Pain medication usage between the two groups will be analyzed with two-tailed unpaired t test, again with results considered statistically significant for  $p < 0.05$ .

Adverse events will be tabulated by treatment group and will include the number of patients for whom the event occurred, the rate of occurrence, and the severity and relationship to study drug.

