STUDY DESIGN	This study is a prospective, randomized trial to compare cryoanalgesia to standard epidural analgesia for post-operative pain management in patients undergoing minimally invasive pectus excavatum repair (the Nuss procedure). 20 subjects will be randomized in 1:1 ratio to receive cryoanalgesia or epidural analgesia prior to their procedure.
PRIMARY OBJECTIVE	To compare post-operative length of stay in patients receiving cryoanalgesia vs. thoracic epidural analgesia for the Nuss procedure

SECONDARY OBJECTIVES	To compare post-operative pain scores, pain medication usage, side effects, and total cost of hospital stay in patients receiving cryoanalgesia vs. thoracic epidural analgesia for the Nuss procedure
NUMBER OF SUBJECTS	20
SUBJECT SELECTION CRITERIA	
Inclusion Criteria: Otherwise healthy male or female patients with pectus excavatum deformity, scheduled for Nuss procedure for chest wall correction, at least 13 years of age at time of Nuss procedure.
 
Exclusion Criteria:
 
 
• Age less than 13 years at time of surgery
 
• Pre-op pain medication usage
 
• Pectus carinatum
 
• Poland's syndrome or other complex chest wall anomaly
 
• Previous repair of Pectus Excavatum by any technique
 
• Previous thoracic surgery
 
• Congenital heart disease
 
• Bleeding dyscrasias
 
• History of previous problems with anesthesia or major anesthetic risk factors
 
• Pregnancy
 
• Non-English speaker
 

TEST PRODUCT, DOSE, AND ROUTE OF ADMINISTRATION	
AtriCure cryosurgical system (AtriCure, Inc., West Chester, Ohio)
 
The cryoprobe will be applied to the intercostal nerve under thoracoscopic visualization at the level of the incision and 2 interspaces above and below, bilaterally. The temperature and duration of cryoablation therapy is pre-set by the probe and cryosurgical system at 2 minutes to -60°C. Each nerve will receive one cycle of cryoablation.

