#### **3.2 Secondary Objectives**

We also hope to see if there is a difference in post-operative pain, medication usage, side effects, and total hospitalization cost between the two anesthetic methods.

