### **10.2 Visit 2- Surgery and Post-operative hospitalization**

Time of Surgery

1. Urine pregnancy test (females)
2. Open randomization allocation envelope
3. Initial analgesic application (cryoanalgesia or epidural) and Nuss procedure

According to inpatient unit protocol

1. Perform and record vital signs.
2. Perform and record oximetry.

Once per day while inpatient

1. Concomitant medications review.
2. Perform abbreviated physical examination.

Twice-per-day study visits while inpatient

1. Record any Adverse Experiences
2. Administer inpatient survey (see separate document)

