## 14.5 Sample Size and Randomization

We used the UCSF Clinical & Translational Science Institute web-based sample size calculator (<http://www.sample-size.net/sample-size-means/>) to determine study size. Based on previous Nuss procedures over the past 2 years at our institution, we determined the mean length of hospitalization was 7 days, with a standard deviation of 1.3 days. From anecdotal data from our prior experience, as well as from speaking with other surgeons utilizing cryoablation, we expect patients in the cryoanalgesia group to have approximately 2 days shorter hospital stay. With type I error rate of 0.05 and type II error rate of 0.1 (yielding 90% power), our study would need 18 patients total. Allowing for some dropout, we will plan to enroll 20 patients to the study.

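### Section 14.4 tests pain between arms separately at every time point at p < 0.05, with no summary measure or adjustment, and adds within-arm tests that do not address the between-arm objective

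*Combined protocol and SAP*

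**What the plan says.** The Protocol Synopsis gives the secondary objective as "To compare post-operative pain scores, pain medication usage, side effects, and total cost of hospital stay in patients receiving cryoanalgesia" versus thoracic epidural. Section 3.2 puts it the same way: "We also hope to see if there is a difference in post-operative pain, medication usage, side effects, and total hospitalization cost between the two anesthetic" (the sentence ends there but for its last word). Both are between-arm questions.

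Section 14.4, repeated in the Statistics part of the synopsis, plans two kinds of test for pain scores:

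- between arms: "Mann-Whitney rank sum tests (to compare between groups at each time point");
- within each arm: "Wilcoxon signed-rank test (to compare scores within groups over time").

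One rule covers both, "with results considered statistically significant for" p < 0.05. The plan names no main time point, no per-patient summary score, no limit on the number of tests and no multiplicity adjustment. It does not say what the within-arm p-values are for, does not label them descriptive, and plans no between-arm test of change over time.

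Section 10.2 schedules a survey at "Twice-per-day study visits while inpatient", and sections 10.3 to 10.6 add surveys at 2 weeks, 1 month, 3 months and 1 year. The survey's content is in a separate document. Section 14 says that a detailed SAP, which may modify these analyses, will be written before the final data are analysed.

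**The concern.** The plan asks one question about pain and answers it with a series of tests. Each one can be declared significant on its own, and nothing says which carries the conclusion. If the arms truly have equal pain, there are many chances for one time point to cross p = 0.05 and be reported as a difference. If results are mixed, the plan does not say whether pain differed.

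The signed-rank tests do not help with this. Pain is expected to fall after surgery in either arm, so a significant fall within one arm says nothing about cryoanalgesia against epidural.

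At stake is the credibility of the pain result, which is the main support for interpreting any difference in length of stay.

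**Working it through.** **Inputs from the documents.** The synopsis states that "20 subjects will be randomized in 1:1 ratio", so 10 per arm. Surveys are twice daily in hospital (section 10.2). Section 14.5 says "the mean length of hospitalization was 7 days, with a standard deviation of 1.3 days", and expects about 2 days less with cryoanalgesia.

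**Assumptions.** The survey supplies the pain scores. Stays are normal with SD 1.3 in both arms. Scores are continuous, with first-order serial correlation rho between successive assessments. The documents give no rho, so 0.5 to 0.9 is shown. Tests are two-sided. In the discharge case, stay is independent of pain.

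**The plan's own figure.** The only stated calculation is for length of stay: n per arm = 2 × (1.960 + 1.282)² × 1.3² / 2² = 2 × 10.51 × 1.69 / 4 = 8.9, rounded up to 9, or 18 in total. This reproduces section 14.5. The documents give no error rate for the pain tests.

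**Number of tests.** 7 days × 2 per day = 14 inpatient time points. The four follow-up surveys are not counted.

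**Chance of at least one false between-arm result, no true difference.** If the 14 tests were independent, each at exactly 0.05, it would be 1 − 0.95¹⁴ = 1 − 0.488 = 51%. Serial correlation lowers this. Simulated Mann-Whitney tests, 10 per arm, give:

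| Setting | rho 0.9 | rho 0.5 |
|---|---|---|
| 14 time points, all patients present | about 24% | about 41% |
| 14 time points, patients leave at discharge | about 21% | about 34% |
| One test | 4–5% | 4–5% |

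Repeat runs gave 22–24% and 42–43% for complete data, and 22% and 37% with discharge, so these figures are good to about three percentage points. With only eight time points (four days), the chance is still 24–27% at rho 0.7 to 0.5.

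**Who is still in hospital.** Under the planning figures, the share with a stay longer than t days is 1 − Φ((t − mean)/1.3).

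| Day | Cryoanalgesia (mean 5) | Epidural (mean 7) |
|---|---|---|
| 3 | 1 − Φ(−1.54) = 94% | 1 − Φ(−3.08) = 99.9% |
| 5 | 50% | 94% |
| 7 | 6% | 50% |

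Late inpatient tests would compare whoever remains, in very unequal numbers. Up to day 3 both arms are nearly complete.

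**Within-arm tests.** Let p be the chance that one arm's signed-rank test is significant. If both arms have the same true change, exactly one is significant with probability 2p(1 − p). For n = 10 the exact critical value is T ≤ 8 (level 0.0488). Simulation, with d the mean change divided by its SD, gives:

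| d | p | 2p(1 − p) |
|---|---|---|
| 0 | 0.048 | 9% |
| 0.5 | 0.282 | 41% |
| 0.7 | 0.491 | 50% |
| 1.0 | 0.785 | 34% |
| 1.5 | 0.983 | 3% |

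The documents give no SD or expected change for pain, so d is unknown.

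**The case against.** The strongest reply is that the plan already contains a valid between-arm test. The same sentence of section 14.4 gives the treatment comparison to Mann-Whitney and labels the signed-rank test as within groups.

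That reply disposes of a stronger reading. A reader might infer that the plan will set one arm's within-arm result against the other's, with a false difference up to half the time. The documents nowhere say this will be done. The 50% is also the mathematical ceiling of 2p(1 − p), reached near d = 0.7; it falls to 9% with no change and 3% at d = 1.5. A false result favouring cryoanalgesia alone is half of each figure. It is not an error rate of this plan.

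Three further replies have weight. The 14 complete time points are an upper case, since many cryoanalgesia patients should be home before day 7; allowing for this lowers the range but leaves it far above 5%. The pain time points are partly unseen, because the survey is a separate document. And this is a secondary endpoint, with a detailed SAP still promised.

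What does not fall is the number of between-arm tests. Mann-Whitney holds its level for one comparison, and the plan uses it at each time point without choosing among them.

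**Conclusion.** The point holds as one about multiplicity and the lack of a named pain comparison. Followed as written, the between-arm pain tests carry about a 21–34% chance of at least one false significant result when patients leave at discharge on the planning figures, and about 24–41% with 14 complete time points, against about 4–5% for one test. The ranges rest on the assumed serial correlation, on the survey being the source of pain scores, and on normal stays with equal SD.

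The within-arm tests are a lesser matter. They do not answer the stated objective and their purpose is unstated, but the plan does not make them the basis of a treatment claim.

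This should be changed before the SAP is final. The primary t test on length of stay and the sample size are not affected.

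**What to change.** In section 14.4, the synopsis and the SAP:

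1. Name one between-arm test, for example Mann-Whitney, of each patient's mean or time-averaged area-under-curve pain score over a prespecified early inpatient window as the main pain comparison. Choose a window in which nearly all patients in both arms are still in hospital; day 3 meets this on the planning figures. Say how the score is formed for a patient discharged inside the window.
2. Report single time points, including later inpatient days and follow-up visits, as between-arm estimates with intervals and no significance claims.
3. Report within-arm change the same way and drop the signed-rank significance rule.
4. State which survey item is the pain score and when it is recorded.

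The cost is wording; no new patients, visits or data are needed. There are two downsides. Significance claims for particular time points are given up. Also, sections 1 and 1.2 say epidural use is limited to the first two to three post-operative days and that the later transition may lengthen stay. An early window therefore largely covers the time the epidural is in use, and the transition and follow-up pain are described but not tested. The SAP should say so.
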